#### **14.4 Subject information card**

The subject will be provided with a Subject information card including the following information:

- That he/she is participating in a clinical study
- Subject study ID
- That he/she is treated with the IMP
- The name and phone number of the Investigator
- Name and address of the Sponsor

#### **14.5 Subject data protection**

The ICF includes information that data will be recorded, collected and processed and may be transferred to European Economic Area (EEA) or non-EEA countries. In accordance with the European Union Data Protection Directive (95/46/EC) and General Data Protection Regulation (GDPR), the data will not identify any persons taking part in the study.

The potential study subject should be informed that by signing the ICF he/she approves that authorised representatives from Sponsor and CTC, the concerned IEC and CA have direct access to his/her medical records for verification of clinical study procedures. For further details on the subject information and ICF process, refer to Section 14.3.

The subject has the right to request access to his/her personal data and the right to request rectification of any data that is not correct and/or complete in accordance with the European Union Data Protection Directive (95/46/EC) and the request will be raised to the Principal Investigator.

The Investigator must file a Subject Identification List which includes sufficient information to link records, i.e. the eCRF and clinical records. This list should be preserved for possible future inspections/audits but must not be made available to the Sponsor except for monitoring or auditing purposes.

Personal data that are collected in the study such as health information and ethnicity are considered as sensitive personal data. This data will be pseudoanonymised, i.e. personally identifiable information (PII) will be removed and replaced by a unique subject ID and will be processed by the Sponsor and other involved parties during the study. After the study end, only anonymised data, i.e. aggregated data sets, can be used.

For this study, the Sponsor Gesynta AB is the data controller of all data processed during the study (e.g. Trial Master File [TMF], study reports) and CTC AB is the data processor. Any subcontractors used in the study are also data processors.

For data that are processed at the clinic(s) (e.g. medical records and ISF), CTC AB is the data controller.

#### **14.6 Changes to the approved clinical study protocol**

Any proposed change to the approved final CSP (including appendices) will be documented in a written and numbered clinical protocol amendment. All substantial amendments to the protocol must be approved by the appropriate IEC and/or CA before implementation according to applicable regulations.

#### **14.7 Audits and inspections**

Authorised representatives of Sponsor, a CA, or an IEC may perform audits or inspections at the research clinic, including source data verification (SDV). The purpose of an audit or inspection is to systematically and independently examine all study-related activities and documents, to determine whether these activities were conducted, and data were recorded, analysed, and accurately reported according to the protocol, ICH-GCP guidelines and any applicable regulatory requirements. The Investigator will contact the Sponsor immediately if contacted by a CA about an inspection at the centre.

#### **14.8 Insurance**

Subjects will be covered under Gesynta Pharma AB's liability insurance policy through the Swedish Pharmaceutical Insurance (Läkemedelsförsäkringen). The certificate of insurance and an information leaflet containing essential information about the insurance coverage can be provided upon request. The participating subjects are also protected in accordance with national regulations, as applicable. CTC has a company insurance covering services performed by CTC.

## **15 STUDY MANAGEMENT**

### **15.1 Training of study site personnel**

Before enrolment of the first study subject a Sponsor representative or delegate will perform a study initiation visit at the research clinic. The requirements of the CSP and related documents will be reviewed and discussed and the investigational staff will be trained in any study specific procedures and system(s) utilised.

It is the responsibility of the Investigator to ensure that all personnel involved in the study are fully informed of all relevant aspects of the study and have a detailed knowledge of and training in the procedures that are to be executed by them. Any new information of relevance to the performance of this study must be forwarded to the staff involved in a timely manner.

The Investigator will keep a list of all personnel involved in the study together with their function and study related duties delegated. A Curriculum Vitae will be available for all staff to whom study-specific duties are delegated.

### **15.2 Clinical monitoring**

The Sponsor is responsible for securing agreement from all involved parties to ensure direct access to all study related sites, source data/documents, and reports for the purpose of monitoring and auditing by the Sponsor, and inspection by domestic and foreign regulatory authorities.

As defined in the risk-based monitoring (RBM) plan, approved by the Sponsor and provided separately, the responsible Monitor will periodically visit the study site at times agreed upon by the Investigator and the Monitor. At the time of each monitoring visit, the role of the Monitor is (but not limited to) to:

- provide information and support to the investigational team.
- confirm that facilities and resources remain acceptable.
- confirm that the investigational team is adhering to the CSP, applicable SOPs, guidelines, manuals and regulatory requirements.
- verify that data are being accurately and timely recorded in the CRFs and that IMP accountability checks are being performed.
- verify that data in the eCRF are consistent with the clinical records (SDV) in accordance with the RBM plan.
- verify that the correct informed consent procedure has been adhered to for participating subjects.
- ensure that withdrawal of informed consent to the use of the subject's biological samples will be reported and biological samples are identified and disposed of/destroyed accordingly, and that this action is documented and reported to the subject.
- verify that AEs are recorded and reported in a timely manner and according to the CSP.

- raise and escalate any serious quality issues, serious GCP breach and any data privacy breach to the Sponsor.

Centralised monitoring will also be performed continuously by study team members at CTC in accordance with the RBM plan.

When the study has been completed and all queries have been resolved and the database has been locked, the Monitor will perform a close-out visit.

### **15.3 Source data documents**

A separate Origin of Source Data List will be generated for each site before start of enrolment, specifying the location of the source of derived information appearing in the CRF. This document must be signed by the Principal Investigator and the Monitor to confirm agreement before start of recruitment.

Source documents are all documents used by the Investigator or hospital that relate to the subject's medical history, that verifies the existence of the subject, the inclusion and exclusion criteria, and all records covering the subject's participation in the trial. They include laboratory notes, memoranda, material dispensing records, subject files, etc. The eCRF may constitute source data if clearly defined in the Origin of Source Data List.

The Investigator should guarantee access to source documents to the Monitor, CAs and the IECs, if required.

### **15.4 Study agreements**

The Principal Investigator must comply with all the terms, conditions, and obligations of the Clinical Study Agreement for this study.

Agreements between Sponsor and CTC must be in place before any study-related procedures can take place, or subjects be enrolled.

### **15.5 Study timetable and end of study**

The study is expected to start in and be completed by Q2 2020.

A subject considered to have completed the study if he/she has completed all visits in the study including the End-of-Study visit.

The end of the clinical part of the study is defined as the last visit of the last subject participating in the study.

### **15.6 Termination of the study**

The Investigator or the Sponsor may terminate this study prematurely for any reasonable cause. The IEC and CA should be informed promptly. Conditions that may warrant study termination include, but are not limited to:

- The discovery of an unexpected, significant, or unacceptable risk to the subjects enrolled in the study or potential study subjects; or
- A decision by the Sponsor to suspend or discontinue development of the IMP.
- If the CA obtains information that raises doubts about the safety or scientific validity of the clinical study, the CA can suspend or prohibit the study. Before the CA reaches its decision, it shall, except where there is imminent risk, ask the Sponsor and/or the Investigator for their opinion, to be delivered within one week (Directive 2001/20/EC, Article 12, Section 1).

If the study is prematurely terminated or suspended for any reason, the Investigator/institution should promptly inform the study subjects and should assure appropriate follow-up for the subjects.

## **15.7 Reporting and publication**

### **15.7.1 *Clinical study report***

A summarising report must be submitted to the applicable CA and IEC within 12 months after completion of the study (in accordance with LVFS 2011:19, Chapter 9).

A CSR, in compliance with ICH-E3, describing the conduct of the study, any statistical analyses performed and the results obtained, will be prepared by CTC AB. The report will be reviewed and approved by, as a minimum, the Principal Investigator, the Statistician and the Sponsor. The study results will be reported in the EudraCT database per applicable regulations within 12 months after completion of the study.

### **15.7.2 *Annual safety report***

If the study duration exceeds one year, the Sponsor must submit development safety update report (DSUR) to the CA and to the IEC. The report shall summarise all pertinent safety information collected during the reporting period and contain an update of the risk-benefit evaluation if there has been any change since the approval of the clinical study.

### **15.7.3 *Confidentiality and ownership of study data***

Any confidential information relating to the IMP or the study, including any data and results from the study, will be the exclusive property of the Sponsor. The Investigator and any other persons involved in the study are responsible for protecting the confidentiality of this proprietary information belonging to the Sponsor.

### **15.7.4 *Publication***

The results from this study may be submitted for publication at the discretion of the Sponsor.

## **15.8 Archiving**

The Principal Investigator is responsible for maintaining essential documents, (as defined in ICH E6 GCP, Section 8) for 10 years after finalisation of the CSR. This includes any original

source documents related to the study, the Subject Identification List (providing the sole link between named subject source records and anonymous eCRF data), the original signed ICFs and detailed records of disposition of IMP.

It is the responsibility of the Sponsor to inform the Investigator/institution as to when these documents no longer need to be retained.

The Sponsor will archive the TMF in accordance with ICH E6 GCP, Section 8 and applicable regulatory requirements.

The data from the eCRFs will be sent to the Sponsor and a copy will be sent to the clinic and filed in the ISF for archiving for 10 years after finalisation of the CSR.

The completed eCRFs are the sole property of the Sponsor and should not be made available in any form to third parties, except for authorised representatives of appropriate Health/Regulatory Authorities, without written permission from the Sponsor.

## **16 DATA MANAGEMENT**

The data management routines include procedures for handling of the eCRF, database set-up and management, data entry and verification, data validation, QC of the database, and documentation of the performed activities including information of discrepancies in the process. The database, data entry screens, and program will be designed in accordance with the CSP.

Data validation/data cleaning procedures are designed to assure validity and accuracy of clinical data. These procedures consist of computerised online edit checks identifying e.g. data values that are outside the allowed range and SAS-programmed batch checks on data exports. All study-specific and standard data validation programming will be tested in a separate testing environment prior to use on production data.

Detailed information on data management will be described in a study-specific Data Management Plan (DMP).

### **16.1 The web-based eCRF**

Clinical data will be entered into a 21 CFR Part 11-compliant eCRF (Viedoc™) provided by PCG Solutions AB. The eCRF includes password protection and internal quality checks, such as automatic range checks, to identify data that appear inconsistent, incomplete, or inaccurate. Clinical data will be entered directly from the source documents or at bedside (if the eCRF data constitutes source data). Source data are to be defined at the site before inclusion of the first subject (Section 15.3).

Authorised site personnel designated by the Investigator will complete data collection. Appropriate training and security measures will be completed with the Investigator and all authorised trial site personnel prior to the trial being initiated and any data being entered into the system for any study subject.

### **16.2 The entering of data into the eCRF**

All entries, corrections, and alterations are to be made by the Investigator or designee. Neither the Monitor nor any other study team member besides site staff can enter data in the eCRF. All data should be entered in English. The eCRFs should be completed as soon as possible during or after the subject's visit. The Investigator must verify that all data entries in the eCRFs are accurate and correct. If some assessments are not done, or if certain information is not available, not applicable or unknown, the Investigator or assigned clinical staff should record such information in the eCRF. The Investigator will be required to electronically sign off the clinical data. This will be performed by means of the Investigator's unique User ID and password; date and time stamps will be added automatically at time of electronic signature.

### **16.3 The query process**

The Monitor will review the eCRFs and evaluate them for completeness and consistency. Data in the eCRF will be compared with the respective source documents to ensure that there

are no discrepancies for critical data as described in the RBM plan. All entries, corrections, and alterations are to be made by the Investigator or designee. Neither the Monitor nor any other study team member besides site staff can enter data in the eCRF.

If corrections are needed, queries will be raised within the eCRF, either as a result of built-in edit checks or manually raised by the monitor. An appropriate member of the site staff will answer the queries in the eCRF either by correcting the data or by entering a response to the query. The monitor will either approve the answer/correction or re-issue the query.

#### **16.4 Audit trail**

All entries in the eCRF will be fully recorded in a protected audit trail. Once clinical data have been saved, corrections to the data fields will be audit trailed, meaning that the reason for change, the name of the person who made the change, together with time and date will be logged.

#### **16.5 External data**

External data consists of data that are not recorded in the eCRF. Data may be received in electronic format or as a paper printout. Key variables are defined in order to uniquely identify each sample record. File and data formats are agreed with the external data provider.

#### **16.6 Medical coding**

Medical coding will be performed by trained personnel at CTC. AEs and medical/surgical history verbatim terms will be coded using the Medical Dictionary of Regulatory Activities (MedDRA; latest version available at start of coding). Prior and concomitant medications will be coded according to the World Health Organisation (WHO) Anatomic Therapeutic Chemical (ATC) classification system. All coding will be approved by Sponsor prior to database lock.

#### **16.7 Database lock**

When all data have been entered and discrepancies solved, clean file will be declared, the database will be locked and the data will be analysed.

## 17 STATISTICAL METHODS AND DETERMINATION OF SAMPLE SIZE

The principal features of the statistical analysis to be performed are described in this section. A more technical and detailed elaboration of the principal features will be presented in a separate Statistical Analysis Plan (SAP), which will be signed and approved prior to database lock.

Analyses of the primary and secondary endpoints will be performed by CTC.

### 17.1 General

Continuous data will be presented in terms of evaluable and missing observations, arithmetic mean, standard deviation (SD), median, minimum and maximum value. In addition, for the parameters AUC and  $C_{max}$  the geometric mean and coefficient of variation (CV) will be presented.

Categorical data will be presented as counts and percentages. When applicable, summary data will be presented by treatment, and by assessment time. Individual subject data will be listed by subject number, treatment, and, where applicable, by assessment time.

All descriptive summaries and statistical analyses will be performed using SAS Version 9.4 or later (SAS Institute, Inc., Cary, NC).

Baseline will be defined as the last data collection point prior to each administration of IMP.

All hypothesis testing will use a significance level of 5%.

No imputation of missing data will be performed.

### 17.2 Determination of sample size

No formal sample size calculation has been performed for this study. The proposed sample size is considered sufficient to provide adequate information for the study objectives.

Approximately 14 subjects will be dosed to achieve a total of at least 12 evaluable subjects that completed the study. Subjects will be evaluable for safety analysis after receiving 1 dose of the study drug.

### 17.3 Analysis data sets

#### 17.3.1 *Safety analysis set*

The Safety Analysis Set will consist of all subjects who received at least one dose of the IMP.

#### 17.3.2 *PK analysis set - formulation:*

The PK analysis set – formulation will consist of all subjects who received a single dose of both Formulation A and Formulation B, from whom PK blood samples were collected after IMP dosing, and for whom there were no AEs or protocol deviations judged to affect the analysis of the data.

### 17.3.3 ***PK analysis set – food interaction:***

The PK analysis set – food interaction will consist of all subjects who received all three IMP doses, from whom PK blood samples were collected after IMP dosing, and for whom there were no AEs or protocol deviations judged to affect the analysis of the data.

## 17.4 **Description of study population**

### 17.4.1 ***Demographics and baseline characteristics***

Descriptive statistics for demographics, weight and height will be presented.

### 17.4.2 ***Medical/surgical history and prior/concomitant medication***

Medical/surgical history will be presented by system organ class (SOC) and preferred term (PT). Prior/concomitant medications will be presented by ATC level 1, 3 and 5 as applicable.

All data will be listed by subject.

### 17.4.3 ***Treatment compliance***

The number of subjects treated in each treatment period and their individual dose will be listed.

## 17.5 **Analysis of primary endpoints**

### 17.5.1 ***Analysis of pharmacokinetics***

The PK analysis will be based on the PK analysis set and performed by CTC. The PK parameters will be calculated by NCA using the software Phoenix WinNonlin® version 8.1 or later (Certara, U.S.A.).

The NCA PK parameters to be assessed include, but are not limited to:

- $AUC_{0-inf}$
- $AUC_{0-last}$
- $C_{max}$
- $T_{max}$
- $T_{1/2(z)}$
- $CL/F$
- $V_z/F$
- Relative bioavailability for Formulation A versus B and for one of the two formulations in fed versus fasting conditions.
- Comparisons of all relevant PK parameters (*e.g.*,  $AUC$ ,  $T_{max}$ ,  $C_{max}$ ) for Formulation A versus B and for one of the two formulations in fed versus fasting conditions.

Summary statistics for the PK parameters will be presented with number of measurements, arithmetic mean, SD, CV, median, minimum, maximum, geometric mean, geometric CV%, except for  $T_{max}$  for which only median, minimum and maximum will be presented.

The relative bioavailability of GS-248 will be analysed with a 90% confidence interval for the ratio of Formulation A and B, and for the ratio of the selected formulation in fed and fasting conditions using a mixed model approach with treatment, period and subject in the model.

Further details will be specified in the SAP.

All data will be listed by subject.

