#### 6.1.6 *Clinical experience*

A phase 1 first-in-human (FIH) study (GS-1001) has been performed in which GS-248 was dosed as an oral solution in fasting conditions. Of this study, the clinical phase has been completed (both the single ascending dose [SAD] and multiple ascending dose [MAD] part) and the clinical study report (CSR) is under development.

During the SAD part of this study, 6 cohorts of 8 subjects each were randomised to GS-248 and placebo at a 3:1 ratio, resulting in a total of 36 subjects being exposed to GS-248. Data from this part of the study indicate that GS-248 administered orally as single doses (1 mg to 300 mg) in healthy volunteers was safe and well tolerated as assessed by reported adverse events (AEs), vital signs, electrocardiograms (ECGs), physical examinations and safety laboratory parameters. No SAEs, no discontinuations due to AEs, and no other noteworthy safety or tolerability findings were reported at any dose level.

PK analysis demonstrated that GS-248 was rapidly absorbed and reached a maximum plasma concentration between 1 and 2.5 hours after single dose administration. The plasma concentration profiles exhibited a multi-exponential decline and the shape of the curves appeared to be similar between the different dose groups. The apparent total clearance of the drug from plasma following non-intravenous administration (CL/F) and apparent volume of distribution associated with the terminal elimination phase following non-intravenous administration ( $V_z/F$ ) were both high. The terminal half-life was estimated to approximately 10 hours. GS-248 exhibited a large variability in exposure and dose proportionality was indicated.

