#### 8.1.1 Part I: Two formulations of GS-248 in fasting conditions

In Part I of the study, a single oral dose of GS-248 in two different solid formulations will be administered to 14 healthy subjects. All subjects will first receive Formulation A (a lipid-based formulation in a capsule) and then Formulation B (a dry powder in a capsule, see Section 10.1). A wash-out period of at least 4 days will be applied between the IMP administrations. Both doses contain 120 mg GS-248. The rationale for the dose is detailed in Section 8.3.

For Part I, subjects will come to the clinic for 4 visits. At Visit 2, subjects will be admitted to the clinic on the afternoon/evening of Day -1 and will remain at the clinic until Day 2 (24 h post dose) for single dose administration of Formulation A and PK and safety assessments. The subjects must fast for at least 10 hours before the anticipated dosing time on Day 1. Water, but no other drinks, is allowed as desired except for 1 h before and 1 h after dosing. The subjects will be carefully monitored by clinical staff during and after dosing. Vital signs and ECG will be checked at regular intervals as detailed in Table 8.1-2. The subjects will return to the clinic on Day 3 (Visit 3) at 48 h post dose for PK blood sampling and safety assessments, as outlined in Table 8.1-1. Safety assessments include AE reporting, physical

examination, ECG, vital signs, body temperature, and blood sampling for analysis of safety laboratory parameters.

Visit 4 will be similar to Visit 2, at which subjects will stay overnight at the clinic from Day -1 to Day 2 for single dose administration of Formulation B and PK blood sampling and safety assessments. Visit 5 will be similar to Visit 3, at which subjects return to the clinic on Day 3 for PK blood sampling and safety assessments.

The schedule of events for Part I is shown in Table 8.1-1 and detailed for visit 2-7 in Table 8.1-2.

Study assessments are described in Section 11.

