### 8.1.2 ***Part II: Food interaction***

After evaluation of the PK profiles of Formulation A and B in Part I of the study, one formulation will be selected to be given following intake of a standardised breakfast in Part II of the study. In this part, any potential food interaction with GS-248 will be investigated.

After evaluation of the PK results from Part I, subjects will return to the clinic for a second dose of the selected formulation (Visit 6, similar to Visit 2), yet this time in fed conditions. The assessments during fed conditions will be the same as during fasting conditions (see Section 8.1.1), except for the fact that the subjects will consume a high-fat high-calorie breakfast 30 minutes prior to IMP administration as detailed in Section 10.5.

At 48 h post dose, subjects will return to the clinic for PK blood sampling and final end-of-study safety assessments (Visit 7).

The schedule of events for Part II is shown in Table 8.1-1 and detailed for visit 2-7 in Table 8.1-2.

Study assessments are described in Section 11.

Table 8.1-1 Schedule of events

Visit	Refer to CSP section	Screening	Part I						Part II	
		Visit 1 Day -28 to -1	Formulation A		Wash-out >4 days	Formulation B		Wash-out and PK calc >14 days	Formulation A or B fed	
			Visit 2 	Visit 3 		Visit 4 	Visit 5 		Visit 6 	Visit 7 
			In-clinic			In-clinic			In-clinic	
Assessment		Day -1 to 2	Day 3	Day -1 to 2	Day 3	Day -1 to 2	Day 3			
Informed Consent	14.3	X								
Inclusion/exclusion criteria	9.4, 9.5	X	X 							
Demographics	11.2.3	X								
Medical/surgical history	11.2.5	X								
HIV, hepatitis B and C	11.2.7	X								
Alcohol breath test	11.2.10	X	X		X			X		
Weight/height (BMI)	11.2.4	X							X 	
Pregnancy Test 	11.2.8	X	X		X			X	X	
Urine Drug Screen 	11.2.9	X 	X	X	X	X		X	X	
Physical Examination	11.4.2	X	X 		X 			X 	X	
Laboratory Safety	11.4.6	X	X	X	X	X		X	X	
Vital Signs	11.4.3	X	X	X	X	X		X	X	
Body temperature	11.4.4		X	X	X	X		X	X	
12-lead ECG	11.4.5	X	X	X	X	X		X	X	
Baseline symptoms	11.2.11	X	X							
IMP administration	10.5		X		X			X		
PK blood sampling 	11.3.1		X	X	X	X		X	X	
Breakfast (standardised)	10.5							X		
Other meals (standardised) 			X		X			X		
Prior/concomitant med.	11.2.6		----- X -----							
AEs 	11.4.1		----- X -----							

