## 8.2 Rationale for study design

The European Medicines Agency (EMA) guideline on strategies to identify and mitigate risks for FIH and early clinical trials with IMPs (EMA/CHMP/SWP/28367/07 Rev. 1) has been considered.

The design of the study is based on the aim to study PK, safety and tolerability of two formulations of GS-248 in a limited number of healthy volunteers. The time points for PK blood sampling have been selected based on data obtained from pre-clinical studies and the FIH study (GS-1001).

A one-sequence design was chosen for the food interaction part of the study to yield a more efficient comparison of treatments than a parallel study design, *i.e.*, fewer subjects might be required since each subject will serve as his own control. To avoid carryover effects, a washout period of at least 4 days has been incorporated between the three treatment administrations. Interim analysis of the FIH study (GS-1001) revealed that none of the subjects receiving multiple doses of 180 mg GS-248 had plasma levels over 5% of  $C_{max}$  at 48 h after the last dose, which indicates that a 4-day wash-out period should be sufficient.

The phototoxicity of GS-248 has not been investigated but based on the MEC value obtained from absorbance studies and the weak and comparatively short-lived potential binding of radioactivity to melanin-containing tissues of the ocular bulb, a phototoxic potential cannot be excluded. Thus, sun protection, as defined in Section 9.6.1, should be used during the study.

GS-248 is a low solubility compound with pH-dependent solubility. A high pH may decrease absorption and thus exposure. For this reason, use of antacids, proton pump inhibitors (PPIs) or any medication that changes gastric pH is not allowed from 14 days prior to IMP administration and until the end-of-study visit.

Overall, the study will provide important data to support the design of further studies, both in healthy volunteers and in patients.

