3 INTRODUCTION

This statistical analysis plan gives details regarding the statistical analyses and data presentation outlined in the final clinical study protocol (CSP) for the study *GS-1002*. Any changes from the final CSP are given in Section 9.

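### Treatment and period are fully aliased, so the protocol's model with period cannot estimate either primary ratio; the SAP drops period without recording the change or stating the no-period-effect assumption

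*Protocol*

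**What the plan says.** The treatment order is the same for everyone. Protocol 8.1.1: "All subjects will first receive Formulation A (a lipid-based formulation in a capsule) and then Formulation B". Protocol 8.1.2 adds a third period: "After evaluation of the PK results from Part I, subjects will return to the clinic for a second dose of the selected formulation", this time fed. SAP 4.5 gives randomisation as not applicable.

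Protocol 17.5.1 obtains the 90% confidence intervals for A/B and for fed/fasting "using a mixed model approach with treatment, period and subject in the model". Protocol 7.1.1 lists both relative bioavailabilities under the primary endpoints.

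SAP 8.1.1.1 instead fits treatment and subject, both fixed, in PROC MIXED, and reports a p-value for each treatment comparison. SAP section 3 promises: "Any changes from the final CSP are given in Section 9". In the text supplied, section 9 is a heading followed directly by section 10, and Appendix 2 (13.2) is a heading followed directly by section 14. Neither carries a redaction mark. The version history mentions only minor adjustments.

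On the design rationale, Protocol 8.2 says: "A one-sequence design was chosen for the food interaction part of the study". It compares this with a parallel design and relies on the wash-out to deal with carryover. It gives no reason for the fixed A-then-B order in Part I and does not discuss period effects.

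**The concern.** A period effect is a change in measured exposure between occasions that the treatment did not cause. A wash-out addresses carryover, which is a different matter. If every subject has the same treatment in the same period, no analysis of these data can separate the two effects. The model named in the protocol then has no solution for the quantities it is meant to deliver. The SAP's model does have one, but what it estimates is treatment multiplied by period.

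A reader of the SAP would not learn this. Its null hypothesis in 4.3 concerns formulation and fed/fasting state only, and its p-values are labelled as treatment differences. Both ratios are primary. The shift is systematic, so a larger sample does not reduce it.

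The plan itself creates one possible source of a period difference. Part I results are evaluated before Visit 6, so fed plasma is assayed later than its fasting comparator. Table 8.1-1 also labels the interval before the fed period "Wash-out and PK calc >14 days", against more than 4 days between A and B.

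**Working it through.** The plan states no figure to reproduce: there is no sample-size calculation (Protocol 17.2) and no period effect. The check has two parts.

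**1. Estimability**

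Inputs: 14 subjects dosed (Protocol 9.3), the fixed order A, B, fed (8.1.1, 8.1.2), subject as a fixed effect (SAP 8.1.1.1). A contrast is estimable only if appending it as a row to the design matrix leaves the rank unchanged. Columns are intercept + 13 subject + treatment + period.

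| Design and model | Columns | Rank | Estimable contrasts |
|---|---|---|---|
| A, B with period | 1+13+1+1 = 16 | 15 | B−A: no |
| A, B, fed with period | 1+13+2+2 = 18 | 16 | none of the three |
| A, B without period | 15 | 15 | B−A: yes |
| A, B, fed without period | 16 | 16 | all three |
| Two sequences AB/BA, with period | 16 | 16 | B−A: yes |
| AB/BA, then fed, with period | 18 | 17 | B−A: yes; both fed contrasts: no |

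In the actual design, adding period adds no rank, so period and treatment are completely aliased.

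The protocol does not say whether period is fixed or random. A random period effect makes the contrast computable but does not resolve the confounding. In one simulated data set (one sequence, n = 12, assumed within-subject CV 30% and between-subject SD 0.5), the REML log-likelihood was 9.7524 at period SDs of 0, 0.02, 0.05, 0.10 and 0.20. The standard error of B−A (log scale) was 0.120, 0.123, 0.139, 0.185 and 0.307 respectively. The likelihood is flat, so the data cannot choose among these standard errors.

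**2. Size of the unstated assumption**

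The documents give neither a period effect nor a within-subject CV. Protocol 6.1.6 says "GS-248 exhibited a large variability in exposure" but does not split within- from between-subject variation. Everything below is therefore assumed: period 2 exposure higher by a fraction d, true A/B = 1.00, and a pairwise analysis with n−1 degrees of freedom.

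- Expected A/B = 1/(1+d): 1/1.05 = 0.952; 1/1.10 = 0.909.
- σ_w = √ln(1+CV²). At CV 30%: √ln 1.09 = 0.294.
- SE = σ_w·√(2/n). At n = 12: 0.294 × √(2/12) = 0.120.
- 90% CI factor = exp(t·SE), with t = 1.796 on 11 df: 1.240.
- Shift relative to the CI half-width on the log scale: ln 1.05/ln 1.240 = 0.227; ln 1.10/ln 1.240 = 0.443.
- Coverage from the non-central t distribution with shift ln(1+d)/SE:

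| n | CV | d = 2% | d = 5% | d = 10% |
|---|---|---|---|---|
| 12 | 20% | 89.1% | 84.6% | 70.2% |
| 12 | 30% | 89.6% | 87.5% | 80.7% |
| 12 | 50% | 89.8% | 89.0% | 86.4% |
| 14 | 30% | – | 87.1% | 79.0% |

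At CV 30%, coverage is slightly worse with 14 subjects than with 12, because the interval narrows while the shift stays the same. A simulation of 200,000 runs at n = 12, CV 30% gave 87.5% and 80.6% for one sequence at d = 5% and 10%. An AB/BA design with period in the model gave 90.0% in both cases, with a mean ratio of 1.00.

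Fed/fasting: a 5% rise per period turns a true 1.00 into 1.05 if B is selected (period 3 against 2), or 1.05² = 1.10 if A is selected (period 3 against 1).

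Price of AB/BA at n = 12, CV 30%: one degree of freedom (11 to 10), so the CI factor goes from 1.240 to 1.243.

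**The case against.** The strongest reply is that the working analysis is sound. Protocol 17 and 17.5.1 leave detail to the SAP, and the SAP fits the only estimable model, so both ratios can be computed. The design is not hidden: one-sequence is in the study title, and the order is stated openly. The study has no equivalence margin and no acceptance limit, and the protocol sets no formal hypothesis. Under Protocol 8.4 the Part II formulation is chosen on PK parameters, not on the interval or p-value. The period effects and CVs used here are assumed. The late-assay mechanism applies only to fed/fasting, and the assay is to be validated.

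Much of this stands. No ratio is uncomputable under the SAP, no bias is shown, and single doses, wash-out and standardised meals limit what a period effect could be. Using the pooled three-period residual (22 df) instead of the pairwise one barely matters: coverage at CV 30% and d = 10% moves from 80.7% to 80.1%. Loss of section 9 text in the PDF reading cannot be wholly excluded.

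Two things do not fall away. Removing a named term from the primary model is a change, not a detail, and the SAP says where changes are recorded. And calling a study one-sequence does not tell the reader that its treatment p-values rest on the absence of a period effect.

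**Conclusion.** The concern holds. With period fixed, the protocol's model cannot estimate either primary ratio; with period random, the period variance is not identifiable. The SAP's model is the right one for the design, but in the text supplied its departure from the protocol is unrecorded and the assumption it needs is unstated. The aliasing follows from the design and needs no numerical assumption.

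The practical size is unknown. Over assumed within-subject CVs of 20–50% with 12 subjects, a 2% period effect is negligible (coverage 89.1–89.8%), 5% gives 84.6–89.0%, and 10% gives 70.2–86.4%. This is a limit on interpretation that should be stated. The change is worth making, but the results are not invalidated.

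**What to change.** **If dosing has taken place in the fixed order, as the SAP's past tense indicates.** Leave the protocol text as it is.

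- Add to SAP section 9: *Period was removed from the CSP 17.5.1 model because it is fully aliased with treatment in this one-sequence design.*
- Add to SAP 8.1.1.1 and to the study report: *Both ratios, their 90% CIs and p-values are valid only if there is no period effect, which this design cannot test.*

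Cost: a new SAP version with one row in its Table 1, and one sentence in the report. No protocol amendment.

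**At protocol stage.** Randomise the Part I order (7 subjects A then B, 7 B then A) and keep period in the A/B model fitted to Part I data. Fed stays in period 3, so drop period from the fed/fasting model and state that this ratio assumes no period effect; it remains confounded.

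Cost: a 14-line randomisation list, one degree of freedom, and both formulations on site at Visit 2 (the documents do not say whether that was possible). The one-sequence wording in the title, synopsis, 8.1 and Table 8.1-1 would also change. If the protocol is already approved, section 14.6 applies: a change "will be documented in a written and numbered clinical protocol amendment". No extra subjects, visits or samples are needed.
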